3.1.5. Pharmacokinetic Analysis Set

The Pharmacokinetic (PK) Analysis Set includes all enrolled patients who receive at least 1 dose of magrolimab and have at least 1 measurable (non-below the limit of quantitation [BLQ] numeric values) post-treatment serum concentration of magrolimab.

3.1.6. Immunogenicity Analysis Set

The Immunogenicity Analysis Set includes all enrolled patients who receive at least 1 dose of magrolimab and have at least 1 reported anti-magrolimab antibody test result.

3.2. Subject Grouping

For analyses based on the Full Analysis Set, patients will be grouped according to the treatment to which they were assigned. For analyses based on the Safety Analysis Set, patients will be grouped according to the actual treatment received. The actual treatment received will differ from the assigned treatment only when their actual treatment differs from assigned treatment for the entire treatment duration.

For the PK Analysis Set and the Immunogenicity Analysis Set, patients will be grouped according to the actual treatment they received.

3.3. Strata and Covariates

This study does not use a stratified randomization schedule when enrolling patients. No covariates will be included in efficacy and safety analyses.

3.4. Examination of Subject Subgroups

Subgroup analyses based on baseline characteristics will not be explored.

3.5. Adjustment for Multiplicity

This study is **CCl** /proof-of-concept in nature and therefore no formal adjustments for multiplicity are made.

3.6. Missing Data and Outliers

3.6.1. Missing Data

In general, missing data will not be imputed unless methods for handling missing data are specified. Exceptions are presented in this document.

Imputation rules for missing date of birth are described in Section 3.7. For missing last dosing date of study drug, imputation rules are described in Section 5.2.1. The handling of missing or incomplete dates for initial AML diagnosis is described in Section 5.4, for date of death and the start date of new anti-AML therapy in Section 6.2.1, for AE onset in Section 7.1.5.2, and for prior and concomitant medications in Sections 5.10.1 and 5.10.2, respectively.

3.6.2. Outliers

Outliers will be identified during the data management and data analysis process, but no sensitivity analyses will be conducted. All data will be included in the data analysis.

3.7. Data Handling Conventions and Transformations

The following conventions will be used for the imputation of date of birth when it is partially missing or not collected:

- If only month and year of birth is collected, then "15" will be imputed as the day of birth
- If only year of birth is collected, then "01 July" will be imputed as the day and month of birth
- If year of birth is missing, then date of birth will not be imputed

In general, age collected at Day 1 (in years) will be used for analyses and presented in listings. If age at Day 1 is not available for a patient, then age derived based on year of birth and the Day 1 visit date will be used instead. If an enrolled patient was not dosed with any study drug, the enrollment date will be used instead of the Day 1 visit date. For screen failures, the date the first informed consent was signed will be used for the age derivation. Age required for longitudinal and temporal calculations and analyses (e.g., estimates of creatinine clearance, age at date of AE) will be based on age derived from date of birth and the date of the measurement or event, unless otherwise specified.

Non-PK data that are continuous in nature but are less than the lower limit of quantitation (LOQ) or above the upper LOQ will be imputed as follows:

• A value that is 1 unit less than the lower LOQ at the same precision level of the originally reported value will be used to calculate descriptive statistics if the datum is reported in the form of "< x" (where x is considered the lower LOQ). For example, if the values are reported as < 50 and < 5.0, values of 49 and 4.9, respectively, will be used to calculate summary statistics. An exception to this rule is any value reported as < 1 or < 0.1, etc. For values reported as < 1 or < 0.1, a value of 0.9 or 0.09, respectively, will be used to calculate summary statistics.

- A value that is 1 unit above the upper LOQ will be used to calculate descriptive statistics if the datum is reported in the form of "> x" (where x is considered the upper LOQ). Values with decimal points will follow the same logic as above.
- The lower or upper LOQ will be used to calculate descriptive statistics if the datum is reported in the form of " \leq x" or " \geq x" (where x is considered the lower or upper LOQ, respectively).

If methods based on the assumption that the data are normally distributed are not adequate, analyses may be performed on transformed data or nonparametric analysis methods may be used, as appropriate.

3.8. Analysis Visit Windows

3.8.1. Definition of Study Day

Study day will be calculated from the first dosing date of study drug (ie, the first dosing date of any study drug) and derived as follows:

- For postdose study days: Assessment Date First Dosing Date + 1
- For days prior to the first dose: Assessment Date First Dosing Date

Therefore, study day 1 is the day of first dose of any study drug administration.

3.8.2. Analysis Visit Windows

Patient visits might not occur on protocol-specified days. Therefore, for the purpose of analysis, observations will be assigned to analysis windows. The analysis windows for lab are provided in Table 3-1 and Table 3-2.

Table 3-1. Analysis Visit Windows for Lab (Excluding Hemoglobin) By-visit Summary

		Visit Window Study Day		
Analysis Visit	Nominal Study Day	Lower Limit	Upper Limit	
Baseline			1ª	
Week 1	8	1 ^b	11	
Week 2	15	12	18	
Week 3	22	19	25	
Week 4	29	26	32	
Week 5	36	33	39	
Week 6	43	40	46	
Week 7	50	47	53	
Week 8	57	54	63	
Week 10	71	64	77	
Week xx (every other week from Week 10)	xx*7 + 1	xx*7-6	xx*7+7	

a Prior to first dose date/time of any study drug

Table 3-2. Analysis Visit Windows for Hemoglobin By-visit Summary

	Nominal Study Visit or	Visit Window Study Day		
Analysis Visit	Study Day	Lower Limit	Upper Limit	
Baseline			1ª	
Day 1 post-dose	Set 1 Day 1, post-dose Unscheduled ^c , post-dose	1 ^b	1	
Day 2	2	2	2	
Day 3	3	3	3	
Day 4 pre-dose	Set 1 Day 4, pre-dose Unscheduled ^d , pre-dose	NA	NA	
Day 4 post-dose	Set 1 Day 4, post-dose Unscheduled ^e , post-dose	NA	NA	
Week 1	8	5	11	
Week 2	15	12	18	
Week 3	22	19	25	
Week 4	29	26	32	
Week 5	36	33	39	

b Post first dose date/time of any study drug

	Nominal Study Visit or Study Day	Visit Window Study Day		
Analysis Visit		Lower Limit	Upper Limit	
Week 6	43	40	46	
Week 7	50	47	53	
Week 8	57	54	63	
Week 10	71	64	77	
Week xx (every other week from Week 10)	xx*7 + 1	xx*7-6	xx*7+7	

a Prior to first magrolimab date/time if the patient is infused with magrolimab, otherwise use first dose date/time of any study drug

Any data relating to unscheduled visits will not be assigned to a particular visit or time point. However, the following exceptions will be made:

- An unscheduled visit prior to the first dosing of study drug will be included in the calculation of the baseline value, if applicable.
- Unscheduled visits after the first dosing of study drug will be included in determining the maximum postbaseline toxicity grade and anti-magrolimab antibody status.
- Response assessments performed at unscheduled visits after the date of first dose of study drug will be included in the analyses of the efficacy endpoints.

3.8.3. Selection of Data in the Event of Multiple Records in an Analysis Visit Window

If multiple valid, nonmissing measurements exist in an analysis window, records will be chosen based on the following rules if a single value is needed:

• For baseline, except hemoglobin, the last nonmissing value on or prior to the first dosing date of study drug will be selected, unless specified differently. If there are multiple records with the same time or no time recorded on the same day, the baseline value will be the arithmetic average of the measurements for continuous data, or the measurement with the lowest severity (eg, normal will be selected over abnormal for safety electrocardiogram [ECG] findings) for categorical data.

b Post first magrolimab date/time if the patient is infused with magrolimab, otherwise use first dose date/time of any study drug

c Hemoglobin collected at unscheduled post-dose visit on the same day of Set 1 Day 1 post-dose visit is mapped to Day 1 post-dose.

d Hemoglobin collected at unscheduled pre-dose visit on the same day of Set 1 Day 4 pre-dose visit is mapped to Day 4 pre-dose.

e Hemoglobin collected at unscheduled post-dose visit on the same day of Set 1 Day 4 post -dose visit is mapped to Day 4 post -dose.

- For hemoglobin baseline (numerical value or grade), if a subject was not infused with magrolimab, the last nonmissing value on or prior to the first dosing date of study drug will be selected. If a subject was infused with magrolimab, the last nonmissing hemoglobin value on or prior to the first magrolimab dosing date will be selected. If there are multiple records with the same time or no time recorded on the same day, the baseline value will be the arithmetic average of the measurements for continuous data, or the measurement with the lowest severity for categorical data.
- For postbaseline values:
 - The record closest to the nominal day for that visit will be selected.
 - If there are 2 records that are equidistant from the nominal day, the later record will be selected.
 - If there is more than 1 record on the selected day, the arithmetic average will be taken for continuous data and the worse severity will be taken for categorical data, unless otherwise specified.

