7.2.1. Summaries of Numeric Laboratory Results

Descriptive statistics will be provided by cohort for laboratory tests (eg, chemistry, hematology, coagulation) as follows:

- Baseline value
- Postbaseline maximum value
- Postbaseline minimum value
- Change and percentage change from baseline to postbaseline maximum value
- Change and percentage change from baseline to postbaseline minimum value

A baseline laboratory value will be defined as the last measurement obtained on or prior to the date/time of first dose of study drug. Change from baseline to a postbaseline visit will be defined as the postbaseline value minus the baseline value. The mean, median, Q1, Q3, minimum, and maximum values will be displayed to the reported number of digits; StD values will be displayed to the reported number of digits plus 1.

Median (Q1, Q3) of the observed values will be plotted using a line plot by cohort and visit for the laboratory tests including but not limited to hemoglobin, platelet and absolute neutrophil counts.

In the case of multiple values associated with a visit, data will be selected for analysis as described in Section 3.8.3.

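### The SAP states the hemoglobin baseline cut-off in three conflicting ways, and the date-only rule in Section 3.8.3, if applied alone, could admit a Day 1 post-dose sample as baseline.

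*SAP*

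**What the plan says.** Three places in the SAP define a baseline that applies to hemoglobin.

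- **Section 3.8.3, hemoglobin bullet:** "If a subject was infused with magrolimab, the last nonmissing hemoglobin value on or prior to the first magrolimab dosing date will be selected". The cut is a date, with no clock time and no pre-dose condition. The bullet says it covers both the numerical value and the grade.
- **Section 3.8.2, Table 3-2, footnote a:** "Prior to first magrolimab date/time if the patient is infused with magrolimab, otherwise use first dose date/time of any study drug". The anchor is the same, but the cut is a date and time.
- **Section 7.2.1:** "A baseline laboratory value will be defined as the last measurement obtained on or prior to the date/time of first dose of study drug". The cut is a date and time, but the anchor is study drug rather than magrolimab. No hemoglobin exception is stated.

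Table 3-2 also has an analysis visit for a hemoglobin drawn after dosing on Day 1 ("Set 1 Day 1, post-dose"). Its window opens after the first magrolimab dose (footnote b: "Post first magrolimab date/time if the patient is infused with magrolimab"). Unscheduled samples follow the same path (footnote c: "Hemoglobin collected at unscheduled post-dose visit on the same day of Set 1 Day 1 post-dose visit is mapped to Day 1 post-dose").

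For ties, 3.8.3 deals with "multiple records with the same time or no time recorded on the same day" by averaging continuous data and taking the least severe category for categorical data.

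**The concern.** A post-dose hemoglobin is planned on the day of the first magrolimab dose. A baseline rule that ends at midnight of that day, not at the start of the infusion, can therefore select a value already lowered by the first dose. The error would run one way: it would shrink the recorded fall.

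Three outputs subtract or compare with baseline. They are the change to postbaseline minimum (7.2.1), the treatment-emergent laboratory grade, which needs a worsening of at least one grade over baseline (7.2.2.1), and the shift from baseline grade to worst grade (7.2.3). The early hemoglobin course clearly matters to the sponsor, since Table 3-2 gives it separate visits for Days 1 to 4 that Table 3-1 does not give to other tests.

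Separately, two anchors (first magrolimab and first study drug) leave hemoglobin with two possible baselines wherever those doses differ in time.

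**Working it through.** No stated design figure bears on this point, so there is nothing to reproduce. The check traces the Day 1 records through each rule and then applies simple arithmetic to an assumed fall.

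**Step 1. Which record is baseline for a patient infused with magrolimab who has a pre-dose and a post-dose hemoglobin on the day of the first infusion?**

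| Rule | Cut | Baseline record |
|---|---|---|
| 3.8.3 sentence alone | first magrolimab date | post-dose (the last value that day) |
| Table 3-2, footnotes a to c | first magrolimab date/time | pre-dose |
| 7.2.1 | first study drug date/time | last value up to first study drug; the same pre-dose record only if no hemoglobin was drawn between first study drug and first magrolimab |

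**Step 2. Size if the 3.8.3 sentence is used alone.** The SAP gives no size for the Day 1 fall, so the values here are assumptions: pre-dose 9.0 g/dL, post-dose 9.0 − d, later nadir 7.0.

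- Pre-dose baseline: change = 7.0 − 9.0 = −2.0, whatever d is.
- Post-dose baseline: change = 7.0 − (9.0 − d) = −(2.0 − d).
- Average of the two records (times missing, both treated as baseline candidates): baseline = 9.0 − d/2, change = −(2.0 − d/2).

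| Assumed d (g/dL) | Pre-dose baseline | Averaged baseline | Post-dose baseline |
|---|---|---|---|
| 0.5 | −2.0 | −1.75 | −1.5 |
| 1.0 | −2.0 | −1.5 | −1.0 |
| 1.5 | −2.0 | −1.25 | −0.5 |

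The understatement is d with a post-dose baseline and d/2 with an averaged one. Neither depends on the assumed 9.0 or 7.0.

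**Step 3. Effect on grade.** With a post-dose baseline, a patient who worsens by one grade between the two Day 1 samples and goes no further shows no rise over baseline. That patient is not counted as treatment-emergent under 7.2.2.1. With missing times the tie rule takes the lower severity, which is the pre-dose grade when hemoglobin falls, so the grade is not masked. The numeric baseline (an average) and the baseline grade (pre-dose) can then rest on different records.

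**Step 4. Anchor.** A hemoglobin drawn after the first study drug but before the first magrolimab infusion belongs to the baseline period under Table 3-2 and 3.8.3, and is postbaseline under 7.2.1. How often this happens depends on dosing order and timing, which the SAP does not show.

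**The case against.** The strongest reply is that the plan already excludes the post-dose sample. The lead-in to 3.8.3 confines its rules to a choice within a window: "If multiple valid, nonmissing measurements exist in an analysis window, records will be chosen based on the following rules". Footnote a closes the hemoglobin baseline window before the infusion, footnote b opens the next window after it, and footnote c sends even unscheduled post-dose values to that next window. On this reading the post-dose sample never becomes a baseline candidate. Section 7.2.1 also cuts by time, so two of the three places agree on a time cut.

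This is the better reading of intent, and it stands. It does not close the matter, for four reasons.

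- Table 3-2 is titled for the by-visit summary, while the exposed outputs are not by-visit.
- The 3.8.3 hemoglobin bullet claims both value and grade and does not say that Table 3-2 prevails.
- A date/time cut cannot be applied when the time is missing, and the averaging rule does not exclude records labelled post-dose.
- The window argument leaves the different anchor in 7.2.1 unresolved.

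A reader might infer more than the document supports:

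- *That the plan makes the post-dose sample the baseline for every patient who has one.* It does so only if the 3.8.3 sentence is programmed without the Table 3-2 window.
- *That the anemia adverse-event-of-interest counts are biased.* Section 7.1.7.3 identifies these by MedDRA search terms, and treatment emergence of adverse events depends on onset date (7.1.5.1). Laboratory baseline plays no part.
- *That other laboratory tests are distorted in the same way.* The wording for them in 3.8.3 is also date-only, against a date/time cut in Table 3-1. But Table 3-1 lists no Day 1 post-dose visit, and the SAP does not show that such samples are scheduled.

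**Conclusion.** The inconsistency is real: a date cut in 3.8.3, a date/time cut in Table 3-2, and a date/time cut on a different anchor in 7.2.1. The intent to exclude post-dose values is visible, so this is a wording defect that permits a wrong derivation. It does not prescribe one.

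If the 3.8.3 sentence is applied alone to outputs that are not by-visit, the change from baseline is understated by d, and some one-grade worsenings are missed. If times are missing and same-day records are averaged, the numeric fall is understated by d/2. This rests on hemoglobin falling by d between the two Day 1 samples, and the SAP gives no value for d.

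Severity is minor to moderate. Laboratory outputs are descriptive and untested (7.2). The CR rate, the adverse-event-of-interest counts, the postbaseline minimum itself and plots of observed values do not subtract the laboratory baseline.

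**What to change.** 1. **Section 3.8.3, hemoglobin bullet:** define baseline as the last nonmissing hemoglobin before the date/time of the first magrolimab infusion, or of the first study drug if magrolimab was not infused. State that this applies to every hemoglobin output, by-visit or not.
2. **Missing times:** let the nominal pre-dose or post-dose label decide. A sample labelled post-dose is never baseline and never enters the same-day average.
3. **Section 7.2.1:** replace the baseline sentence with a reference to 3.8.3, so that hemoglobin has one anchor throughout. Because 7.2.1 now holds the date/time cut for the other tests, put the same cut into the other-laboratory bullet of 3.8.3; otherwise the reference would loosen their rule.

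The cost is a few lines of text and a small derivation change. No new data are needed, since Table 3-2 already relies on times and pre-dose/post-dose labels. Section 1 says that changes after SAP finalization are documented in the CSR, so the clarification can go there if the SAP is not reissued. For outputs already produced, list any baseline hemoglobin that is labelled post-dose or timed after the start of the first infusion. An empty list shows that the Table 3-2 rule was used in practice.

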3.9. Assessment of COVID-19 Impact

This study was ongoing during the novel coronavirus (COVID-19) pandemic which has an impact on the study conduct. Some patients may have been unable to attend onsite visits due to shelter in place guidelines, site closures, or other reasons. The following special situations due to COVID-19 will be handled in the analysis:

- Study treatment discontinuation due to COVID-19
- Protocol deviations due to COVID-19
- Missed or Virtual Visits due to COVID-19
- Adverse events due to COVID-19

4. PROTOCOL DEVIATIONS

A by-patient listing will be provided for those patients who did not meet at least 1 eligibility (inclusion or exclusion) criterion but enrolled in the study. The listing will present the eligibility criterion (or criteria if more than 1 deviation) that patients did not meet and related comments, if collected.

Protocol deviations occurring after patients entered the study are documented during routine monitoring. The number and percentage of patients with important protocol deviations, and the number and percentage of patients with important protocol deviations by deviation reason (e.g., nonadherence to study drug, violation of select inclusion/exclusion criteria) will be summarized by cohort for the All Enrolled Analysis Set. A by-patient listing will be provided for those patients with important protocol deviation.

5. SUBJECT INFORMATION

5.1. Patient Enrollment and Disposition

A summary of patient enrollment will be provided by cohort for each country, investigator and overall. The summary will present the number and percentage of patients enrolled. For each column, the denominator for the percentage calculation will be the total number of patients analyzed for that column.

A summary of patient disposition will be provided by cohort. This summary will present the number of patients screened, the number of patients enrolled, and the number of patients in each of the categories listed below:

- All Enrolled Analysis Set
- Full Analysis Set
- Safety Analysis Set
- DLT-evaluable Analysis Set
- Completed study treatment (magrolimab, azacitidine, venetoclax, mitoxantrone, etoposide, cytarabine)
- Discontinued study treatment (magrolimab, azacitidine, venetoclax, mitoxantrone, etoposide, cytarabine) with reasons for discontinuation
- Completed Study
- Discontinued study with reasons for discontinuation

For the status of study drug and study completion and reasons for discontinuation, the number and percentage of patients in each category will be provided. The denominator for the percentage calculation will be the total number of patients in the Full Analysis Set corresponding to that column.

The following information will be provided in by-patient listings by patient ID number in ascending order to support the above summary tables:

- Reasons for study drug discontinuation
- Reasons for study discontinuation

5.2. Extent of Study Drug Exposure

Extent of exposure to study drug will be examined by assessing the total duration of exposure to study drug and relative dose intensity. Each variable will be calculated for magnolimab, venetoclax, azacitidine, mitoxantrone, etoposide and cytarabine. No formal statistical testing is planned.

5.2.1. Duration of Exposure to Study Drug

Total duration of exposure to study drug (magrolimab, venetoclax, azacitidine, mitoxantrone, etoposide and cytarabine) will be defined for a patient as last dosing date minus first dosing date plus 1 day, regardless of any temporary interruptions in study drug administration, and will be expressed in weeks using up to 1 decimal place (eg, 4.5 weeks).

The total duration of exposure to each study drug will be summarized using descriptive statistics for continuous variables, as well as using the number and percentage of patients exposed for at least the following time periods: 1 day, 1 week, 4 weeks, 8 weeks, 12 weeks, 16 weeks, 20 weeks, 24 weeks, etc. Summaries will be provided for the Safety Analysis Set. If the last study drug dosing date is missing,

- If the study drug is permanently withdrawn, the latest date among the study drug end date, start date of AE leading to study treatment discontinuation, clinical visit date, laboratory sample collection date, and vital signs assessment date that occurred during the on-treatment period will be used for subjects included in the final analyses or the last available date in the database for subjects who were still on treatment at the time of final analysis.
- If the study drug completion status is unknown, the earlier of the date of death or data snapshot date for analysis will be used.

The number of cycles patients were exposed to venetoclax, azacitidine, mitoxantrone, etoposide and cytarabine will be summarized using descriptive statistics, as well as the number and percentage of subjects exposed to a given cycle category (eg, ≥ 1 , ≥ 2 , ≥ 3 , etc).

The number and percentage of patients who have planned dose level different from the standard protocol dose level, infusion interruption, dose modification, dose delay, or dose missed for study drug and the reasons will be summarized.

A by-patient listing of magrolimab administration will be provided by cohort, patient ID number (in ascending order) and visit (in chronological order).

